### 13.11 Secondary Statistical Analyses of Primary Effectiveness Endpoint

#### 13.11.1 Per-Protocol Analysis

This analysis will be performed in the PP subject population. Propensity score weighting methodology will be applied to adjust for the imbalance of subjects' characteristics between these two groups. Cross-over subjects will be added to the ablation group and the time-dependent covariate will be used to account for the different timing of cross-over. A propensity score weighted Cox proportional hazards model will be used to compare the hazard rate between the two groups at observed death times. Diagnosis analyses will be performed to examine the assumption of proportional hazards. If the proportional hazards assumption is not met, then the interaction effect of time by treatment group and other remedy analyses will be investigated. The adjusted hazard ratio and its 95% confidence intervals will be reported for the two groups. Missing primary effectiveness endpoint data and the associated covariates that will be included in the propensity score modeling will be imputed using the multiple imputation method.

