2.2 Efficacy, Safety and Health Economic Endpoints

2.2.1 Efficacy Endpoints

The primary efficacy endpoint is the time to persistent AF/AT (excluding isthmus-dependent atrial flutter) at 3 years. According to the protocol, persistent AF/AT is defined as AF/AT lasting longer than 7 consecutive days or requiring termination by cardioversion after 48 hours.

Secondary efficacy endpoints are:

- Rate and time to persistent AF/AT at 1 year and 2 years, rate of persistent AF/AT by number of ablations at 3 years
- Number of repeat ablations and new anti-arrhythmic drugs (AAD) per subject throughout 3 years follow-up

- Rhythm (% subjects in sinus rhythm (SR), % subjects with recurrent AF/AT) throughout 3 years follow-up
- Factors associated with AF disease progression
 - Gender
 - Age
 - Left atrium (LA) size
 - HATCH score (score based on the five components: Hypertension, Age 75 years or older, Previous transient ischemic attack or stroke, Chronic obstructive pulmonary disease, and Heart failure)
 - Blood pressure
 - NYHA functional classification of heart disease
 - Presence of diabetes
 - Presence of hyperlipidemia or dyslipidemia
 - Presence of renal insufficiency
 - Presence of dementia

In addition, an alternative definition of the primary and the first secondary endpoint will be investigated based on the consensus statement of the HRS (Heart Rhythm Society, 2017). According to the HRS consensus statement 2017, persistent AF/AT is defined as continuous AF/AT that is sustained beyond 7 days.

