where M is the updated sample size per group, N is the initially planned sample size per group, δ is the expected effect size (1.1541) and Δ is the effect size observed at the time of interim analysis:

$$\Delta = -\log_e \left(\frac{D_t/T_t}{D_c/T_c} \right)$$

where D_t and D_c are the number of deaths observed in the treatment and control group and T_t / T_c are the total times observed (up to the time of censoring) in the respective groups.

In case the re-estimated sample size is unrealistic high, the sponsor will select one of the following 3 options:

- Determine the maximum realistic sample size and continue the study to enroll the maximum number of patients
- Continue study as planned to enroll original planned sample size
- Stop the study for futility.

In case the sample size will be increased, the CHW (Cui, Hung and Wang) adaptive method will be used for statistical testing.⁶

The CHW weighting will be applied according to the following formula:

$$Z = \sqrt{t_{adj}} Z_{0;adj} + \sqrt{(1 - t_{adj})} Z_{adj;max}$$

Where Z is the final test statistic, t_{adj} is the (planned) information fraction at the time of sample size adjustment, $Z_{0;adj}$ is the test statistic derived from the data available at the time of sample size adjustment, and $Z_{adj;max}$ is the test statistic derived from data collected after the time of sample size adjustment, including a possibly increased sample.

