10.1 Primary Efficacy Variable Analysis

The primary analysis will be a Kaplan-Meier (KM) analysis for all subjects in the ITT population and account for censored observations. The primary effectiveness analysis will be performed in the ITT population, where the subjects will be attributed to the treatment group as randomized, regardless of treatment cross-over or post-randomization medical care. A log-rank test will be used to compare the hazard functions between the two groups at any observed event time. If observed, the median time to persistent AF/AT as well as the 95% confidence intervals will be reported by treatment group based on Kaplan-Meier estimates. The rate of survival without persistent AF/AT and rate of persistent AF/AT at 3 years follow-up as well as the 95% confidence intervals for both groups will be presented using the product limit estimate from the Kaplan Meier curve. Kaplan-Meier curves will be plotted.

The effect size is defined as the negative log of the hazard ratio (hazard rate of the Test Group over hazard rate of the Control Group): $\delta = -\log_e(\lambda_t/\lambda_c)$.

This study is to test the following hypothesis using a one-sided test at alpha equal to 0.025:

H0: $\delta \leq 0$

H1: $\delta > 0$

Null hypothesis: the hazard rate in the Test Group is greater than or equal to the hazard rate in the Control Group at observed event times during the follow-up period

Alternative hypothesis: the hazard rate in the Test Group is less than the hazard rate in the Control Group at observed event times during the follow-up period

Subjects will be considered to have an effectiveness success if they do not progress to persistent AF/AT through the 3-year follow-up period.

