10.2 PP analysis

The Kaplan-Meier analysis as described in section 10.1 will be repeated in the PP population (based on the as-treated principle).

Moreover, an inferential analysis using a Cox proportional hazards model will be performed in the PP subject population. For the Cox proportional hazards model, treatment itself will be modelled as a time-dependent covariate, i.e:

- for control group (without cross-over): treatment at time t is “control” at any time t
- for ablation group (without cross-over): treatment at time t is “ablation” at any time t
- for cross-over group: treatment at time t is control at any time t before cross-over and ablation at any time t after cross-over

The Cox proportional hazards model will be used to compare the hazard rate between the two treatment groups at observed event times.

The hazard ratio and its 95% confidence interval will be reported. Missing primary effectiveness endpoint data will be censored at the time of the subject’s last visit/TTM.

The same principles outlined for section 10.1 also apply for section 10.2 (PP analysis).

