14.2 EFFICACY DATA				
14.2.1.1	ITT	Time to Persistent AF/AT (Primary Efficacy Analysis) Results of Kaplan-Meier analysis and log rank test	16.2.17.1	2.1 (but without rates at 3 years and incl. conditional power)
14.2.1.2	ITT	Time to Persistent AF/AT (Primary Efficacy Variable)	16.2.17.1	2.2

Table Number	Population	Table Title / Summary	Supporting Listing	Interim Analysis Number
		Recalculated Operating Characteristics for Group Sequential Design		
	ITT	Time to Persistent AF/AT (Primary Efficacy Variable) Sample Size Re-Estimation	16.2.17.1	2.3 Only required for first interim analysis; not required for final analysis
14.2.1.3	ITT	Time to Persistent AF (HRS 2017) Results of Kaplan-Meier analysis and log rank test	16.2.17.1	
14.2.2.1	PP	Time to Persistent AF/AT Results of Kaplan-Meier analysis and log rank test	16.2.17.1	
14.2.2.2	PP	Time to Persistent AF/AT Cox regression analysis including treatment as time-dependent covariate	16.2.17.1	
14.2.2.3	PP	Time to Persistent AF (HRS 2017) Results of Kaplan-Meier analysis and log rank test	16.2.17.1	
14.2.2.4	PP	Time to Persistent AF (HRS 2017) Cox regression analysis including treatment as time-dependent covariate	16.2.17.1	
14.2.3.1	ITT	Time to Persistent AF/AT: Subgroup analyses Results of Kaplan-Meier	16.2.17.1	

Table Number	Population	Table Title / Summary	Supporting Listing	Interim Analysis Number
		analysis		
14.2.3.2	ITT	Time to Persistent AF (HRS 2017): Subgroup analyses Results of Kaplan-Meier analysis	16.2.17.1	
14.2.4.1	ITT, PP	Time to Persistent AF/AT by Number of Repeat ablations Results of Kaplan-Meier analysis	16.2.17.1	
14.2.4.2	ITT, PP	Time to Persistent AF/AT at 1 Year Results of Kaplan-Meier analysis and log rank test	16.2.17.1	
14.2.4.3	ITT, PP	Time to Persistent AF/AT at 2 Years Results of Kaplan-Meier analysis and log rank test	16.2.17.1	
14.2.4.4	ITT, PP	Time to Persistent AF (HRS 2017) by Number of Repeat ablations Results of Kaplan-Meier analysis	16.2.17.1	
14.2.4.5	ITT, PP	Time to Persistent AF (HRS 2017) at 1 Year Results of Kaplan-Meier analysis and log rank test	16.2.17.1	
14.2.4.6	ITT, PP	Time to Persistent AF (HRS 2017) at 2 Years Results of Kaplan-Meier analysis and log rank test	16.2.17.1	
14.2.5	ITT, PP	Number of Repeat Ablations	16.2.17.3	

Table Number	Population	Table Title / Summary	Supporting Listing	Interim Analysis Number
14.2.6	ITT, PP	Number of New AAD Drugs per Subject	16.2.17.3	
14.2.7	ITT, PP	Summary of Dose changes	16.2.22	

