15.2 Planned Listing Descriptions

The following are planned data and subject listings for protocol 144 (09-Apr-2013). Listings will number according to the nomenclature used to support the clinical study report. Listings will be ordered by treatment group and subject and timepoint. In addition to the unique subject identification, the treatment group will be displayed on all listings.

It is indicated in the last column which listings will also be produced for interim analysis.

Listing Number	Population	Listing Title / Summary	Interim Analysis
16.2.1	All Subjects	Study Population Status for Each Subject	
16.2.2	ITT	Inclusion/Exclusion Criteria for Each Subject	
16.2.3	ITT	Study Completion Status and Discontinued Subjects	
16.2.4.1	Screening Failures	Reason for Screening Failures	
16.2.4.2	ITT	Protocol Deviations Reported in CRF	
16.2.4.3	ITT	Major Protocol Deviations and Exclusions from Analysis Populations	
16.2.5	ITT	Visit Dates Including Days since Randomization	
16.2.6	ITT	Subject Demographics	
16.2.7	ITT	Cardiovascular Medical History	
16.2.8	ITT	Other Relevant Medical History	
16.2.9	ITT	Prior Procedure History	
16.2.10	ITT	AF History	
16.2.11	ITT	Cardiovascular Medication History	
16.2.12	ITT	Screening Examination Done (Yes/No)	

Listing Number	Population	Listing Title / Summary	Interim Analysis
16.2.13	ITT	AFEQT Questionnaire	
16.2.14	ITT	EQ-5D Questionnaire	
16.2.15	ITT	Ablation Procedures	
16.2.16	ITT	Baseline Medication Optimization	
16.2.17.1	ITT	Primary Endpoint: Time to Persistent AF/AT	3.1
16.2.17.2	ITT	CEC Adjudication Form	
16.2.17.3	ITT	Secondary Endpoints - Number of repeat ablations and new anti-arrhythmic drugs and heart rhythm	
16.2.18	ITT	Follow-Up Visits – Assessments Performed	
16.2.19	ITT	Blood Pressure	
16.2.20	ITT	NYHA Classification and Additional Diagnoses	
16.2.21	ITT	HATCH Score	
16.2.22	ITT	Cardiovascular Medication	
16.2.23	ITT	Adverse Events	3.2
16.2.24	ITT	Serious Adverse Events Form	
16.2.25	ITT	Unscheduled Cardiovascular Visit/Hospitalization	
16.2.26	ITT	12-Lead ECG	
16.2.27	ITT	Holter Monitoring	
16.2.28	ITT	Event Recorder	
16.2.29	ITT	Transesophageal Echocardiogram	
16.2.30	ITT	Transthoracic Echocardiogram	
16.2.31	ITT	Cardioversion	

Listing Number	Population	Listing Title / Summary	Interim Analysis
16.2.32	ITT	Medication Management	

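### SAP section 6 miswords the event counts in the sample-size re-estimation formula as deaths; they should be persistent AF/AT events

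*SAP*

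**What the plan says.** The re-estimation in SAP section 6 runs once, at the first interim analysis. If conditional power lies between 0.3 and 0.9, the new size per group is M = N(δ/Δ)², with N = 161 and δ = 1.1541. Δ "is the effect size observed at the time of interim analysis" and is calculated as −log[(D_t/T_t)/(D_c/T_c)]. The SAP then states that D_t and D_c "are the number of deaths observed in the treatment and control group", and that T_t and T_c are total observed times that run to censoring.

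Other places bear on what D should mean:

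- SAP 2.2.1: "The primary efficacy endpoint is the time to persistent AF/AT (excluding isthmus-dependent atrial flutter) at 3 years".
- SAP 10.1, in the primary efficacy analysis: "The effect size is defined as the negative log of the hazard ratio", Test over Control.
- SAP 15.1, title of the re-estimation output (interim output 2.3): "Time to Persistent AF/AT (Primary Efficacy Variable) Sample Size Re-Estimation". Its supporting listing is 16.2.17.1.
- SAP 15.2, title of listing 16.2.17.1: "Primary Endpoint: Time to Persistent AF/AT".
- Protocol 13.11.1, on the per-protocol Cox model for the same endpoint, says it will "compare the hazard rate between the two groups at observed death times". SAP 10.2 rewords this to "compare the hazard rate between the two treatment groups at observed event times".

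**The concern.** D_t and D_c are the only event counts in Δ, and Δ is the only effect estimate that enters M. The protocol describes re-estimation (13.4) without a formula, so SAP section 6 is the one place where D is defined. Taken literally, that definition sets a mortality effect against a design effect for AF progression, and M then means nothing.

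The SAP replaced the same word in the per-protocol analysis, but left it here, where it defines a decision formula. The result of that formula can lead to a larger trial, to CHW weighting of the final test or, if M is too large to be practicable, to a sponsor choice that includes stopping for futility.

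The definition of T has a smaller fault. Time should stop at the event for a subject who progresses, and the sentence names only censoring.

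**Working it through.** **1. What the design effect measures.** Inputs from SAP section 6: 3-year progression of 5% (Test) and 15% (Control after cross-over).

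- Hazards: −ln(0.95)/3 = 0.01710 and −ln(0.85)/3 = 0.05417 per year.
- δ = ln(0.05417/0.01710) = 1.153. The SAP states 1.1541; the difference of under 0.1% is immaterial.

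**2. Reproducing 322.** Further inputs from SAP section 6: one-sided alpha 0.025, power 85%, 10% drop-out over 3 years (hazard −ln(0.9)/3) and 1.5 years of accrual. I assume uniform accrual followed by 3 more years of follow-up.

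- Event probabilities: 0.0582 (Test) and 0.1723 (Control).
- n per arm = (1.960 + 1.036)²/1.153² × (1/0.0582 + 1/0.1723) = 155.3, or 312 in total. An assumed 3% group-sequential inflation gives 320, against 322 stated.
- Power at 161 per arm is 0.862 against 1.96 and 0.842 against the planned final bound of 2.0507.

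So δ and N rest wholly on AF/AT progression. M compares like with like only if D counts the same event. If Δ = 1.1541, then M = 161 and nothing changes.

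**3. What the counts do to M.** The documents give no interim counts, so these are illustrations with equal person-time and δ = 1.1541.

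| Counts, Test v Control | Δ | M per group |
|---|---|---|
| 1 v 4 | ln 4 = 1.386 | 161 × (1.1541/1.386)² = 112 (no increase) |
| 2 v 3 | ln 1.5 = 0.405 | 1305 |
| 1 v 2 | ln 2 = 0.693 | 447 |
| 1 v 1 | 0 | infinite |
| 0 in either arm | undefined | undefined |

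**4. Literal reading beside the correct one.** Assume a first look at 12 months and uniform accrual of 322 over 18 months. Person-time is 322 × (12/18) × 0.5 = 107 years, or 53.7 per arm. Counts are taken as Poisson.

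- Δ is undefined with probability 1 − (1 − e^−a)(1 − e^−b), where a and b are the expected counts per arm.
- M exceeds 2N when |Δ| < 1.1541/√2 = 0.816.
- Expected progressions are 53.7 × 0.01710 = 0.92 (Test) and 53.7 × 0.05417 = 2.91 (Control). The mortality rates are assumptions, equal in both arms.

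| What D counts | Expected total | Δ undefined | M > 2N when Δ is defined |
|---|---|---|---|
| Deaths, 1% per year | 1.1 | 83% | 94% |
| Deaths, 2% per year | 2.1 | 57% | 84% |
| Deaths, 3% per year | 3.2 | 36% | 76% |
| Persistent AF/AT at the design hazards | 3.8 | 43% | 57% |
| Persistent AF/AT, 5 events as in the SAP 10.4 example, split in the same ratio | 5 | 32% | 48% |

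These figures ignore the requirement that conditional power lie between 0.3 and 0.9.

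**5. The point about T.** At the same look there are about 107 subjects per arm with follow-up spread evenly over 0 to 1 year. The time wrongly added after events is about 107 × hazard/6, or 0.3 years (Test) and 1.0 year (Control), against 53.7 per arm. Δ moves by about ln(54.7/53.7) − ln(54.0/53.7) ≈ 0.01.

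**The case against.** The strongest reply is that context settles the meaning. Δ is the observed effect size, SAP 10.1 defines effect size within the primary efficacy analysis, and the re-estimation output is titled for time to persistent AF/AT and drawn from the primary endpoint listing. A programmer working from that output and listing would count AF/AT events. The protocol's use of death times for the same endpoint suggests leftover survival-analysis vocabulary. All of this stands, and it shows that AF/AT events were intended. It does not make the sentence right, because no other text defines D.

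A second reply is that much of the instability under deaths is ordinary sparsity at an early look. This also stands. With the correct counts Δ is still undefined in about 43% of cases, which is more than the 36% for deaths at 3% per year. The figures for deaths should not be quoted without that comparison. The timing is assumed as well: SAP 10.4 leaves the looks unfixed and offers the 12-month schedule as an example.

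A third reply is that little remains to act on. SAP 5.1 records early termination, and SAP 15.1 requires the re-estimation output only at the first interim analysis. This stands for the final analysis, unless the sample size was in fact changed; the documents do not say.

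The point about T is answered in part by SAP 8.3, which applies censoring only to subjects in whom the endpoint was not observed.

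**Conclusion.** The wording is wrong and should be corrected. SAP section 6 says deaths where it must mean primary endpoint events, in the only formula that sets M. It is a minor drafting error in an operative decision rule.

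A reader might infer that the sample size was re-estimated on mortality. The documents do not support that: the effect-size definition, the output title and the source listing all tie the calculation to persistent AF/AT, and nothing shows that deaths were counted. A reader might also take the high failure rates under deaths as the harm done by the word. The comparison in the working shows that correcting it would leave much of that instability in place.

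The planned 322 is unaffected. The effect on the actual M cannot be given without the interim counts. The percentages rest on a 12-month look, uniform accrual, Poisson counts, equal person-time and assumed mortality. The fault in T is negligible at that look, with a change in Δ of about 0.01.

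**What to change.** In SAP section 6, define D_t and D_c as the numbers of sponsor-adjudicated primary endpoint events (persistent AF/AT) in each group. Define T_t and T_c as total time from randomization to the event or censoring, whichever comes first. Randomization is the start date that SAP 8.3 reports for the interim analyses.

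Then check that the first-interim program used these counts and times, and report the counts. This shows whether any increase in sample size, and the CHW weighting that it would trigger, had a valid basis.

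The cost is one sentence in the SAP and one program check. The planned sample size does not change. The final analysis would need another look only if the check finds that the sample size was altered on the wrong counts.

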7. ANALYSIS POPULATIONS

The following analysis populations will be used to complete the analyses of data.

Cross-over subjects will be handled differently for each type of analysis population, as described subsequently. In general, subjects from the control group who have an ablation procedure after the primary endpoint is met will not be analyzed as cross-over.

Intent to treat (ITT) population: The ITT subject population will include all

subjects randomized, where subjects will be classified by the group to which they are randomized, regardless of the treatment received. For the ITT population, cross-over subjects will be included in the Control Group per randomization. Lost-to-follow-up and withdrawn/early termination subjects will also be included in the ITT population.

Per protocol (PP) population: The PP subject population will include randomized subjects who satisfy the following criteria, according to the treatment actually received:

- **Test Group:** subjects who
 - have undergone RF ablation,
 - are treated with the study catheter (THERMOCOOL[®] Catheter Family),
 - are in compliance (no major protocol deviations that has an impact on scientific value of the study) with the study protocol, and
 - have been treated for the study-related arrhythmia.
- **Control Group:** subjects who
 - have started an investigator-prescribed AAD and completed the dose-loading period (2 weeks),
 - have not undergone RF ablation,
 - are in compliance (no major protocol deviations that have an impact on scientific value of the study) with the study protocol, and
 - have been treated for the study-related arrhythmia.

All analyses conducted in the PP population will be as treated analyses. For descriptive tables and simple inferential models with fixed treatment effects subjects who have undergone RF ablation will be included in the Test Group regardless of the original treatment assigned (original randomization). Thus, cross-over subjects will be included in the Test Group for PP analyses. For more complicated inferential analyses, models will be applied where treatment itself is included as time-dependent covariate (see section 10.2 and 10.6.4). The approach described above applies for all tables which do not summarize data by visit (e.g. for time to event endpoints and other endpoints calculated overall per-patient). For summaries by visit and repeated measurement models, cross-over subjects will be completely excluded.

Safety Population: The Safety Population will include all subjects who have undergone insertion of an ablation catheter, either as Test Group or cross-over subjects; and, subjects who started an investigator-prescribed AAD in the Control Group and did not initiate ablation therapy. Analysis of catheter-related complications will be limited to include only subjects who initiated ablation treatment (catheter insertion) either as Test Group and cross-over subjects.

Adverse drug reactions will be analyzed overall for all the subjects who have taken investigator-prescribed AAD and analyzed separately for cross-over subjects, those in the Test and Control Groups (excluding cross-over subjects).

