8. GENERAL ISSUES FOR STATISTICAL ANALYSIS

8.1 General Statistical Methodology

Descriptive summaries will be provided where appropriate for each of the primary and secondary variables. Tables in the ITT population will summarize data by randomized treatment, tables in the PP and Safety populations will summarize data by treatment actually received if not otherwise specified.

Primary and secondary effectiveness analysis will be conducted in the ITT and the PP populations. All safety data analyses will be performed in the Safety Population.

Health economic and QoL tables will be completed for the ITT population unless otherwise specified. According to the protocol it was planned to use the PP population for health economic and QoL tables, but this was changed to ITT population to perform the analysis based on the randomized treatment groups.

Continuous, quantitative, variable summaries will include the number of subjects (N) with non-missing values, mean, standard deviation (SD), median, minimum, maximum, and quartiles, unless otherwise specified.

Categorical, qualitative, variable summaries will include the frequency and percentage (where applicable) of subjects who are in the particular category. In general, the denominator for the percentage calculation will be based upon the total number of subjects in the study population for the treatment groups unless otherwise specified.

The baseline value will be defined as value entered to the screening/baseline page of the eCRF (terminology screening/baseline is not used consistently in eCRF, but there is only one screening/baseline assessment planned according to protocol).

All analyses will be performed using SAS[®] Software version 9.1.3 or later. ADDPLAN[®] version 5.0.2 or later and East version 5.3 or later may also be used.

For re-calculating of operating characteristics for the analyses of the primary endpoint, the software WinLD will be used.

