11.2 Catheter-related complications (AEs)

A key secondary safety endpoint, catheter-related complications (AEs), is limited to subjects who have initiated RF ablation and who are in the safety population. Catheter-related AEs are those AEs that are identified as possibly, probably or definitely related to the study device. The number and percentage of subjects with catheter-related AEs will be summarized by system organ class and preferred term for Test Group and cross-over subjects and overall in the safety population. Moreover, catheter-related complications will be summarized (overall, all types accumulated), in a further table containing the number and percentage of subjects with catheter-related complications by number of repeat ablations, by anticipated or not, by severity and by outcome.

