11.4 Primary AEs

Primary AEs are defined as specific AEs that occur within 7 days of ablation procedure (AE categories as defined in the study protocol).

The number and percentage of subjects with primary AEs will be summarized by system organ class and preferred term, overall and by treatment group.

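### Control subjects ablated after the primary endpoint lose the cross-over label in the SAP, so complications of those ablations are left out of the catheter-related safety tables

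*SAP*

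**What the plan says.** SAP section 7 opens with a remark that cross-over subjects are treated differently from one population to the next. It then gives the rule, introduced as holding in general: "subjects from the control group who have an ablation procedure after the primary endpoint is met will not be analyzed as cross-over". No effectiveness restriction is attached.

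The Safety Population in the same section has two limbs:

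- "all subjects who have undergone insertion of an ablation catheter, either as Test Group or cross-over subjects"
- "subjects who started an investigator-prescribed AAD in the Control Group and did not initiate ablation therapy"

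The analysis of catheter-related complications is then "limited to include only subjects who initiated ablation treatment (catheter insertion) either as Test Group and cross-over subjects". SAP 11.2 repeats that this endpoint "is limited to subjects who have initiated RF ablation and who are in the safety population", and it tabulates Test, cross-over and overall. SAP 8.1 adds: "All safety data analyses will be performed in the Safety Population". The table shells in SAP 15.1 put every 14.3 table on the Safety Population.

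Protocol 13.6 defines the Safety Population with the same two limbs but without the post-endpoint rule. The Cross-over Group in Protocol 13.11.2 and SAP 10.3 carries no condition on endpoint timing. SAP section 5, which lists changes to the planned analysis, does not mention the rule.

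**The concern.** For effectiveness the rule is sound, because an ablation after the event cannot alter the time to that event. For safety the same reasoning does not apply: a complication of a catheter procedure is one whether or not the subject had already progressed.

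The omission is also not random. Every subject left out has already reached persistent AF/AT, and the Protocol's own risk appendix (Appendix A, Precautions) links serious complications to the severity of cardiac disease. What is at stake is the completeness of the ablation complication rate, which SAP 2.2.2 names among the key safety endpoints. On one reading, ablation events would also be displayed under drug therapy.

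**Working it through.** **Step 1. Apply the definitions to one subject.** Take a Control subject who started AAD, reached persistent AF/AT, and then had an ablation catheter inserted.

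| Condition | Source | Met? |
|---|---|---|
| Counts as cross-over | SAP 7, general rule | No |
| Safety limb 1: catheter inserted, as Test or cross-over | SAP 7 | No, if the Test/cross-over phrase is a filter |
| Safety limb 2: Control on AAD, no ablation begun | SAP 7 | No |
| Catheter-complication set: Test or cross-over | SAP 7 | No |

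The last row is the firm result, because it does not depend on how limb 1 is read. The second row depends on the reading.

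**Step 2. Check that the planning inputs are used as the plan uses them.** SAP 6 gives 161 per arm, 50% cross-over, and 3-year progression of 25% on drug and 5% after ablation. The diluted Control rate is 0.5 × 0.25 + 0.5 × 0.05 = 0.15, so 0.85 remain progression-free. That is the figure SAP 6 uses in place of 0.75. Only the first term matters here; the second covers subjects ablated before progressing, who keep the cross-over label.

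**Step 3. Control subjects who progress with no prior ablation.**

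- With 50% cross-over: 161 × 0.5 × 0.25 = 20.1
- With no cross-over: 161 × 0.25 = 40.25

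The second case is a bound. It is relevant because Protocol Appendix B aims to bring cross-over well below published rates.

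**Step 4. Number left out.** The documents do not say what fraction of these subjects is later ablated. I assume 10% to 75%, and that all 161 Test subjects are ablated.

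- With 50% cross-over: 20.1 × 0.10 = 2.0, and 20.1 × 0.75 = 15.1. Other ablated subjects: 161 + 80.5 = 241.5. Share of all ablated: 2.0/243.5 = 0.8%, to 15.1/256.6 = 5.9%.
- With no cross-over: 40.25 × 0.10 = 4.0, and 40.25 × 0.75 = 30.2. Other ablated subjects: 161. Share: 4.0/165.0 = 2.4%, to 30.2/191.2 = 15.8%.

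**Step 5. Effect on the reported rate.** Let the tabulated rate be p, the omitted share s, and the omitted subjects' risk r × p. The full rate is p × (1 + s(r − 1)). If r = 1, the rate is unbiased and only events are lost. If r = 2 (illustrative assumption), the full rate is 1.06 times the tabulated one at s = 5.9%, and 1.16 times at s = 15.8%.

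**Step 6. Overall column in SAP 11.4.** Primary AEs are tied to an ablation by definition (Protocol 12.1.1), yet they "will be summarized by system organ class and preferred term, overall and by treatment group" in the whole Safety Population. If all 322 subjects are in that population and 241.5 are ablated, the overall percentage is 241.5/322 = 0.75 of the rate per ablated subject.

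**The case against.** The strongest reply is that the rule is hedged as general and follows a remark that populations differ, so it may have been meant for effectiveness only. Protocol 11.4.2 also describes cross-over as ablation before the endpoint is reached, so keeping later ablations apart has a basis. Both points are fair. But the Safety Population uses the term cross-over without redefining it, and nothing brings these subjects back.

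A reader might infer that all their adverse events vanish from the safety tables. That needs the phrase about Test or cross-over in limb 1 to act as a filter. It can also be read as explanatory, and SAP 8.1 arranges safety tables by the treatment a subject actually received, which works against exclusion. The documents therefore do not establish a loss of all events. SAP 11.2 taken alone would admit these subjects once they are in the Safety Population, but section 7 expressly limits the catheter analysis to Test and cross-over, so a programmer would have to set that sentence aside.

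A reader might also infer that the events are hidden. They are not. Ablation procedures (listing 16.2.15), AEs (16.2.23) and SAE forms (16.2.24) are on ITT, and SAP 9.1 requires a listing of reasons for exclusion from each population and of the Safety treatment assignment. SAP 7 also foresees an overall ADR analysis of all AAD takers.

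Nor does 11.4 misstate the ablation column, which has its own denominator; only the overall figure is diluted. The Control column is not necessarily empty either: on the looser reading it would hold these subjects' primary AEs.

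Finally, the numbers are small. Protocol Appendix A puts perforation below 1%, so 15 omitted subjects imply fewer than 0.15 expected perforations, and 30 fewer than 0.30. The 10% drop-out, the short follow-up left after late progression, and early termination (SAP 5.1) would lower the counts further.

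**Conclusion.** The concern holds for the catheter-related tables. SAP 7 withdraws the cross-over label from Control subjects ablated after the endpoint and limits catheter-related complications to Test and cross-over subjects, so complications of these ablations are missing from the tables and rates in 11.2 and the catheter-related part of 11.3. In the general AE tables the outcome depends on the reading: exclusion on the literal wording, or display under drug therapy on the looser one.

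The size is about 2–15 subjects (1–6% of all ablated) at planning figures, or 4–30 (2–16%) with no cross-over. Both ranges rest on the assumed 10–75% later ablated, for which the documents give no figure.

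Severity is moderate. A reader might infer that the trial's conclusions are compromised. They are not: the endpoint is secondary and descriptive (Protocol 13.16), the ITT primary analysis and every design figure are untouched, and the listings preserve the events. It remains a stated rule, not declared as a change, that makes a key safety rate selectively incomplete.

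**What to change.** 1. In SAP 7, restrict the sentence on ablation after the endpoint to effectiveness analyses.
2. Define the Safety Population as all randomized subjects with an ablation catheter inserted at any time, plus Control subjects who started AAD.
3. Base the catheter-related tables in 11.2 and 11.3 on all subjects with a catheter inserted, with columns for Test, cross-over before the endpoint, and Control ablated after the endpoint.
4. In the general AE tables (11.1), show the last group separately too, with events split into before and after ablation, so that ablation events do not appear under drug therapy.
5. As a minor presentation point, give the overall primary-AE percentage in 11.4 per subject with a catheter inserted.
6. Record the change in SAP section 5.

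The cost is SAP wording, a population flag and some extra programming. No new data are needed: safety follow-up runs to 3 years after the endpoint (Protocol 11.2.1 and 11.4.2), and ablations and AEs are already listed on ITT. The downside is a possibly slightly higher reported complication rate.
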